 Mount Sinai	Protocol Name:	A double-blinded, placebo-controlled study to evaluate the tolerability and efficacy of Enstilar® (calcipotriene and betamethasone dipropionate) Foam in the treatment of chronic plaque psoriasis in patients with skin of color (Fitzpatrick skin phototypes IV-VI).
	Principal Investigator:	[name], MPH
	Primary Contact Name/Contact Info:	[name], MPH [contact]
	Date Revised:	08/10/2017
	Study Number:	IF2166478

1. Provide written, signed and dated informed consent prior to initiating any study-related activities.
2. Male or female >18 years of age at the time of screening
3. Fitzpatrick Skin phototype IV-VI, non-white race/ethnicity, including but not limited to African Americans, Asians, Pacific Islanders and Hispanics.
4. Clinical diagnosis of chronic plaque-type psoriasis of the body
5. Plaque psoriasis with $\geq 2\%$ Body Surface Area (BSA) involvement (may include scalp involvement), PASI Score ≥ 2 , IGA mod 2011 score of 2 or greater (based on scale of 0-4)
6. Females of childbearing potential (FCBP) must have a negative pregnancy test at Screening and Baseline. While using investigational product and for at least 28 days after last application of investigational product, FCBP who engage in activity in which conception is possible must use one of the approved contraceptive options described below:

Option 1: Any one of the following highly effective methods: hormonal contraception (oral, injection, implant, transdermal patch, vaginal ring); intrauterine device (IUD); tubal ligation; or partner's vasectomy;

OR

Option 2: Male or female condom (latex condom or nonlatex condom NOT made out of natural [animal] membrane [for example, polyurethane]; PLUS one additional barrier method: (a) diaphragm with spermicide; (b) cervical cap with spermicide; or (c) contraceptive sponge with spermicide.
7. Must be in general good health as judged by the Investigator, based on medical history and physical examination. (NOTE: The definition of good health means a subject does not have uncontrolled significant co-morbid conditions).

Exclusion:

1. Form of diagnosed psoriasis other than chronic plaque psoriasis (i.e. guttate, erythrodermic, pustular)
2. Diagnosis of other active, ongoing skin diseases or skin infections that may interfere with examination of psoriasis lesions

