 Mount Sinai	Protocol Name:	A double-blinded, placebo-controlled study to evaluate the tolerability and efficacy of Enstilar® (calcipotriene and betamethasone dipropionate) Foam in the treatment of chronic plaque psoriasis in patients with skin of color (Fitzpatrick skin phototypes IV-VI).
	Principal Investigator:	[name], MPH
	Primary Contact Name/Contact Info:	[name], MPH [contact]
	Date Revised:	08/10/2017
	Study Number:	IF2166478

Proportion of patients at weeks 4 and 8 who achieved treatment success according to scalp investigator global assessment (ScIGA). ScIGA will range from 0 (clear) to 4 (severe). Treatment success is defined as ScIGA of clear (0) or almost clear (1) for patients with \geq moderate disease at baseline or ScIGA of clear (0) for patients with mild disease at baseline.

5. Patient’s Global Assessment of Itch at weeks 1, 2, 4, and 8

The VAS is a numerical scale used to assess patients’ perception of pruritus/itch. Subjects will be asked to complete the VAS scale at all scheduled visits. The evaluation is a 10cm long line on which the subjects indicate the severity of their pruritus from “0” (no pruritus) to “10” (severe pruritus).

**6. Patient’s Global Assessment of disease severity (PaGA) at weeks 4 and 8.
Treatment success will be defined as clear or almost clear**

At weeks 4 and 8, subjects will be asked to assess the severity of their psoriasis on a PaGA patient questionnaire. PaGA will have 5 distinct options ranging from “Clear” to “Severe.” Treatment response will be defined as clear or almost clear disease (for those with moderate or severe disease at baseline) or clear disease (for those with mild disease at baseline).

7. Change in erythema index of target psoriasis plaque from baseline to weeks 2, 4, and 8

A skin spectrophotometer (Mexameter) will be used to quantify the degree of erythema of lesional skin compared to an index area (of unaffected skin) at baseline, week 2, week 4, and week 8. Erythema index will be recorded at these timepoints and compared to baseline measurements.

8. Change in melanin indices of target psoriasis plaque from baseline to weeks 2, 4, and 8

A skin spectrophotometer (Mexameter) will be used to quantify the melanin index (degree of hyperpigmentation or hypopigmentation) of lesional skin compared to an index area (of unaffected skin) at baseline, week 2, week 4, and week 8. Melanin index will be recorded at these timepoints and compared to baseline measurements.

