Photography: Standardized photographs will be taken of the entire body (front and back). The photograph will be taken with the patient standing up in front of a neutral background; photographs will be taken at a standardized distance with the patient facing towards and away from the camera such that the entire body included in the picture. Photographs will be taken at baseline and weeks 4 and 8.

Body Surface Area (BSA): The total body involvement of psoriasis will be recorded as a percentage of the totally BSA at screening, baseline, and weeks 2, 4, and 8.

Investigator's Global Assessment (IGA mod 2011): The IGA mod 2011 is a standardized rating scale for assessment of overall psoriatic disease severity. IGA mod 2011 (entire body including scalp) will be performed by the investigator or designated qualified site staff at screening, baseline, and weeks 2, 4, and 8. If the subject has scalp involvement at the baseline visit, Scalp IGA (ScIGA) will be performed. For ScIGA, the IGA mod 2011 scale will be used to evaluate the severity of psoriasis on the scalp only.

	Protocol Name:	A double-blinded, placebo-controlled study to evaluate the tolerability and efficacy of Enstilar® (calcipotriene and betamethasone dipropionate) Foam in the treatment of chronic plaque psoriasis in patients with skin of color (Fitzpatrick skin phototypes IV-VI).
	Principal Investigator:	[name], MPH
	Primary Contact Name/Contact Info:	[name], MPH [contact]
	Date Revised:	08/10/2017
	Study Number:	IF2166478

The scale is as follows:

Score	Short Description	Detailed Description
0	Clear	No signs of psoriasis. Post-inflammatory hyperpigmentation may be present
1	Almost clear	Normal to pink coloration of lesions; no thickening; no to minimal focal scaling
2	Mild	Pink to light red coloration; just detectable to mild thickening; predominantly fine scaling
3	Moderate	Dull bright red, clearly distinguishable erythema; clearly distinguishable to moderate thickening; moderate scaling
4	Severe	Bright to deep dark red coloration; severe thickening with hard edges; severe / coarse scaling covering almost all or all lesions

Psoriasis Area and Severity Index (PASI) (and Psoriasis Scalp Severity Index (PSSI) if applicable)

The investigator or trained qualified site staff will complete the PASI (and PSSI assessment) at screening, baseline, and weeks 2, 4, and 8.

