Lower Extremities (L)	0 – none 1– slight 2 – moderate 3– severe 4 – very severe	0 – none 1– slight 2 – moderate 3– severe 4 – very severe	0 – none 1– slight 2 – moderate 3– severe 4 – very severe	0– no involvement 1– >0 to <10% 2– 10 to <30% 3– 30 to <50% 4– 50 to <70% 5– 70 to <90% 6– 90 to 100%

When calculating PSSI, similar grading of erythema (E), induration (I), and desquamation (D) will be performed with a scale of 0 (none) to very severe (4). In addition, the extent of scalp involvement (0 to 100%) will be assessed. The area score will be graded in the same manner as the PASI score (1– >0 to <10%, 2– 10 to <30%, 3– 30 to <50%, 4– 50 to <70%, 5– 70 to <90%, 6– 90 to 100%). For those with no scalp involvement (0) at baseline, PSSI will not be performed.

$$\text{PSSI score} = (E_s + I_s + D_s)A_s$$

 Mount Sinai	Protocol Name:	A double-blinded, placebo-controlled study to evaluate the tolerability and efficacy of Enstilar® (calcipotriene and betamethasone dipropionate) Foam in the treatment of chronic plaque psoriasis in patients with skin of color (Fitzpatrick skin phototypes IV-VI).
	Principal Investigator:	[name], MPH
	Primary Contact Name/Contact Info:	[name], MPH [contact]
	Date Revised:	08/10/2017
	Study Number:	IF2166478

Patient Global Assessment of severity (PaGA):

Patient will complete a PaGA questionnaire at baseline, week 2, week 4, and week 8 to ask about severity of their overall clinical condition. The scale will include 5 categorical options – clear, very mild, mild, moderate, and severe.

Short Description	Detailed Description
Clear	No signs of psoriasis at all
Very Mild	Very slight psoriasis symptoms that do not interfere with daily life at all
Mild	Slight psoriasis symptoms that only occasionally interfere with daily life
Moderate	Definite psoriasis symptoms that frequently interfere with daily life
Severe	Intense psoriasis symptoms that very often interfere with or restrict daily life

Subject VAS of pruritus: The VAS is a numerical scale used to assess patients’ perception of pruritus/itch. Subjects will be asked to complete the VAS scale at baseline and weeks 1, 2, 4, and 8. The evaluation is scored from 0 (no pruritus) to 10 (severe pruritus).

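### The scalp IGA (ScIGA) success rule has no provision for a scalp that is only almost clear at baseline, although such subjects enter the endpoint

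*Protocol*

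**What the plan says.** **Entry.** Protocol section 5(b), inclusion criterion 5, sets severity for the whole body: "IGA mod 2011 score of 2 or greater (based on scale of 0-4", with BSA and PASI minima beside it. On the scalp it says only that the disease "may include scalp involvement". No minimum scalp severity appears there or elsewhere in the protocol.

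**Who is scored on the scalp.** In the procedures section, under Investigator's Global Assessment: "If the subject has scalp involvement at the baseline visit, Scalp IGA (ScIGA) will be performed". The instrument is the same five-grade scale: "For ScIGA, the IGA mod 2011 scale will be used to evaluate the severity of psoriasis on the scalp only". Grade 1, almost clear, is described as "Normal to pink coloration of lesions; no thickening; no to minimal focal scaling".

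**Success rule.** Section 5(e), secondary endpoint 4, applies at Weeks 4 and 8: "Treatment success is defined as ScIGA of clear (0) or almost clear (1) for patients with" at least moderate disease at baseline, or "ScIGA of clear (0) for patients with mild disease at baseline". The text does not say whether disease at baseline is that of the scalp or of the whole body.

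**PSSI.** The procedures section also opens PSSI to any scalp involvement: "For those with no scalp involvement (0) at baseline, PSSI will not be performed". Its responder rule is a percentage improvement from the subject's own baseline.

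**The concern.** The two-limb rule was built for an endpoint whose entry criterion rules out baseline grades 0 and 1. Carried over to ScIGA, it meets a population for which grade 1 is not ruled out. Grade 1 still describes lesions, so a scalp can be involved and almost clear at the same time.

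Two things are then undetermined. One is whether a subject who starts at ScIGA 1 can be a success at all. The other is which baseline severity decides the limb that applies. Both feed directly into the scalp success proportions at Weeks 4 and 8. The subset is part of 20 drug and 5 vehicle subjects, so a single subject's classification shows in the result. If the reading is settled only after the data are seen, the choice can follow the result.

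**Working it through.** The protocol gives no figure to reproduce for this endpoint. The check applies the rule as written to each possible combination of baseline and later score, without worsening.

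**Inputs**
- Whole-body IGA at entry: 2, 3 or 4 (inclusion criterion 5).
- Baseline ScIGA in subjects with scalp involvement: 1 to 4 (no minimum stated; grade 1 includes lesions).
- Rule: success is 0 or 1 if the baseline grade is 3 or 4; success is 0 only if the baseline grade is 2; nothing is stated for grade 1.
- Arm sizes: 20 drug, 5 vehicle (opening summary). The number with scalp involvement is not given.

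**Step 1: whole-body IGA (primary endpoint).** Entry grades are 2, 3 and 4, and each falls in a limb. The rule is complete.

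**Step 2: ScIGA under the two possible readings**

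| Baseline | Later ScIGA | Disease = scalp severity | Disease = whole-body severity |
|---|---|---|---|
| IGA 3 or 4, ScIGA 1 | 1 | no limb applies | success, scalp unchanged |
| IGA 3 or 4, ScIGA 1 | 0 | no limb applies | success |
| IGA 2, ScIGA 1 | 1 | no limb applies | not a success |
| IGA 2, ScIGA 1 | 0 | no limb applies | success |
| IGA 2, ScIGA 3 | 1 | success | not a success |
| IGA 3, ScIGA 2 | 1 | not a success | success |

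Under the scalp reading, a subject who clears from 1 to 0 meets no success definition and is a non-success if kept in the denominator. Under the whole-body reading, a subject with IGA 3 or 4 who stays at ScIGA 1 is a success. The last two rows show that the readings also disagree for baseline ScIGA above 1 whenever scalp and whole-body severity fall in different limbs.

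**Step 3: PSSI.** PSSI = (E + I + D) × A. Taking a grade-1 scalp as E 0 or 1, I 0, D 0 or 1 and A 1 to 6 (my mapping of the grade-1 wording), the non-zero baseline values run from (1 + 0 + 0) × 1 = 1 to (1 + 0 + 1) × 6 = 12. Unchanged gives 0% improvement, a non-responder. Cleared gives 100%, a responder for both PSSI50 and PSSI75. Both are classified correctly. The one exception is E = I = D = 0 with some area recorded: baseline PSSI is 0 and the percentage is undefined.

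**Step 4: weight of one subject.** The shift is 100 / n percentage points, with n the number with scalp disease in the arm.
- Vehicle: 100 / 5 = 20 if all five have scalp disease; 100 / 2 = 50 if two do (assumed).
- Drug: 100 / 20 = 5 if all twenty do; 100 / 8 = 12.5 if eight do (assumed).

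**The case against.** The best defence is that the context settles the reading. The success sentence sits in a scalp endpoint, directly after the ScIGA range, and mild and moderate are grade names of the scale being scored. On that reading an unchanged scalp at grade 1 is never a success. The subject at grade 1 simply falls outside the rule, and leaving such a subject out of the denominator is as compatible with the text as counting a failure. Handling of that kind is often left to the analysis plan. The large shifts per subject come from having five vehicle subjects and would arise for any binary endpoint here.

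Much of this stands. The scalp reading is the more natural one, the frequency of baseline ScIGA 1 is unknown, and the small arm drives the size. What does not follow is that nothing needs changing. The protocol itself writes the success definition, and that definition does not fit the population the protocol admits to it. An analysis plan could repair this only by adding to the endpoint.

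A reader might infer more than the text supports in two ways. First, that both errors occur together: they are alternatives, one for each reading. Second, that PSSI50/75 shares the fault because it admits the same subjects. It does not, since it is measured against the subject's own baseline. A low baseline PSSI makes the measure coarse, but an unchanged scalp is still a non-responder and a cleared scalp a responder.

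**Conclusion.** The point holds for ScIGA only. The rule in secondary endpoint 4 does not fit a baseline ScIGA of 1, and it gives a faulty or undefined result for that baseline on either reading of disease at baseline.

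The consequence is limited. It concerns one secondary endpoint in a subset; the primary IGA rule is complete because of the entry threshold. Whether any subject will start at ScIGA 1 cannot be told from the protocol. If one does, the vehicle proportion can move by 20 to 50 points and the drug proportion by 5 to 12.5 points, the upper ends resting on the assumption that 2 of 5 and 8 of 20 subjects have scalp disease. A distorted comparison with vehicle can arise at Week 4 only: after that visit all subjects receive open-label drug, so at Week 8 only the response proportions themselves are affected.

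**What to change.** In section 5(e), secondary endpoint 4:
- State that mild and moderate at baseline mean the baseline ScIGA grade.
- Limit the ScIGA success proportion to subjects with baseline ScIGA of 2 or more, which matches the whole-body entry threshold.
- Keep scoring ScIGA in every subject with scalp involvement, and list those with baseline ScIGA 1 descriptively.

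Leave PSSI50/75 unchanged; restricting it would only drop subjects who are already classified correctly.

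The cost is about two sentences and no new data, since Table 1 already schedules ScIGA at baseline. The downside is a slightly smaller scalp denominator. The change should be made before unblinding.
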